It is well known that internal and external rotation of the shoulder are often limited following reverse total shoulder arthroplasty (RTSA). RTSA can reliably restore active forward elevation, abduction, and external rotation, which are often lost in patients with massive rotator cuff tears. However, functional internal rotation (i.e., functional movements of the hand behind the body) is often unsatisfactorily restored or even lost after RTSA.¹⁻³ Limited internal rotation has been attributed to mechanical impingement of the humeral socket against bony structures or soft tissue. Various biomechanical studies have recently analyzed factors influencing functional internal rotation. These data suggest that lateralization of the center of rotation, inferior positioning of the glenoid component,⁴⁻⁶ a decreased glenosphere size,⁷ a more varus neck-shaft angle,⁸ and less humeral component retroversion⁹⁻¹² are positively associated with improved internal rotation. However, it is not uncommon to observe limited functional internal rotation despite these measures. Limited internal rotation can be disabling for activities such as toileting, pulling up pants or shorts, or tucking in a shirt.^{1-3,13} The authors' intraoperative observation suggests that limited internal rotation is caused by soft tissue restraints rather than impingement of the humeral socket against bony structures. This observation calls for further research.

METHODS

Study design

The following protocol has been developed per Standard Protocol Items: Recommendations for Interventional Trials guidelines. This study will be a prospective randomized-controlled clinical trial (RCT) comparing outcomes after either RTSA or RTSA with conjoint tendon lengthening. The trial will be conducted at a single high-volume academic center in Columbia, Missouri. Blinding in surgical trials is difficult, and neither surgeons nor participants will be blinded to treatment allocation. However, the independent statistician will be blinded to allocation groups.

Recruitment and consent

The study population will consist of participants undergoing RTSA. Eligible participants will be identified at the shoulder and elbow clinic, be invited to take part in the trial, and will be informed of study details and provided with written information along with a detailed explanation of the trial by a member of the research team. Once a participant agrees to participate, and meets all inclusion criteria, they will be enrolled and randomized into one of two groups.

Study participants

Inclusion criteria

- All patients undergoing primary RTSA

Exclusion criteria

- Revision RTSA
- RTSA for acute proximal humerus fracture or fracture sequela

Baseline measures

The following will be collected from all participants preoperatively:

- Age
- Sex
- Preoperative functional (operative) shoulder and contralateral shoulder range of motion if applicable
- Indication for RTSA
- Associated injuries
- Medical comorbidities
- Residence and ambulatory status

Treatment allocation

Individuals consenting to participate in the trial will be randomized to RTSA or RTSA plus conjoint tendon lengthening. Each patient will receive a study ID, and a computer randomization system will be used to allocate patients to receive either of two groups.

Intervention

All RTSAs will be performed by the attending surgeon ([name]) in a standard fashion through a deltopectoral approach. The skin will be incised with bovie electrocautery in standard fashion, and the dissection will be carried down through the subcutaneous tissue to the level of the shoulder. The subscapularis muscle will be incised and reflected to expose the shoulder joint. Following

surgical removal of the humeral head and reaming of the glenoid cavity, the Perform glenoid and humeral components of Tornier Stryker Reverse Shoulder system will be implanted. The sizes and offsets of the components will be chosen based on each patient's local anatomy which will vary among patients. Each of these surgical steps will be performed in all patients regardless of whether they are in the control or investigative group. Following final implant selection, the subscapularis tendon will be repaired using three transosseous nonabsorbable sutures whenever there is a repairable subscapularis tendon. After definitive implantation of the prosthesis is completed, and the subscapularis tendon is reattached, the investigative step will take place. In the control group, which is the group receiving a RTSA without conjoint tendon lengthening the subcutaneous tissue and skin will be closed in standard fashion. In the investigative group, prior to subcutaneous and skin closure, the conjoint tendon will be lengthened by approximately 2 cm. The conjoint tendon is comprised of the coracobrachialis and biceps short head tendon, which attach proximally to the coracoid process at the level of the shoulder. In the investigative group, as mentioned, the conjoint tendon will be released completely via a Z-shaped incision made at a level 2 cm distal to the coracoid process and sutured back in a lengthened position using #2 Ethibond suture for the patients assigned the conjoint lengthening group. Electrocautery will be used for the lengthening, and the underlying muscular portion of the conjoint tendon will be preserved. As mentioned above, the control group will not receive this conjoint tendon lengthening. Then, for the investigative group following lengthening and like the control group, the wound will be closed in layers, and the shoulder will be immobilized in an abduction sling.

Postoperative management

Postoperatively, patients will wear the sling for 4 weeks, after which supervised physical therapy will begin.

Outcome measures

The primary outcome will be functional internal rotation at six months. Functional internal rotation will be measured based on the highest anatomical level that the patient's thumb can reach:

- Side
- Ipsilateral buttock
- Lower lumbar
- Mid-lumbar
- Upper lumbar
- Thoracolumbar junction
- T10 and above

Additional secondary outcome measures and associated timepoints will include:

- Six weeks: pain VAS
- Three months: pain VAS, ASES, SANE, Forward elevation, external rotation at the side
- Six months, one year, and two years: pain VAS, ASES, SANE, PROMIS, VR-12, Forward elevation, external rotation at the side
- Complications at any time points: dislocation, severe pain, arm muscle cramping, implant loosening, infection, hematoma, medical complications, blood transfusions, non-union, mortality rate. Specific surgical complications include wound infections, intraoperative fracture, deep surgical infection, and periprosthetic fractures.

Follow-up

All participants will be surveilled per standard of care at our hospital for the targeted patient group. Patients will return for follow-up at two weeks, six weeks, three months, six months, one year, and two years. Plain radiographs will be taken at the immediate postoperative (anesthesia care unit) setting and at all scheduled follow-up visits. Radiographs obtained in clinic at the aforementioned follow-up intervals are standard of care and are not part of the research explicitly. For example, all patients regardless of whether they are in the control or investigative group will receive radiographs at the above intervals. A member of the research team will review participant outcome measures at each appointment.

Sample size calculation

To reject the null hypothesis that functional internal rotation is equal between groups, 32 subjects are needed per group with a power set at 80%, and with a Type 1 error probability of 5%.

Data collection and management, and risks

Data collection will primarily be electronically based. A breach of confidentiality and/or privacy is a risk of this study. To prevent this, all collected data will be stored electronically in password-protected files to protect patient identity and information. All information will be collected and reviewed by the research team only. Data will be maintained on a password-protected computer that will be accessible only to the study team. No patient identifiers will be maintained in the database. Every attempt will be made to minimize missing data. Multiple contact details will be taken at recruitment, and a system of reminders plus phone contact if applicable will be made to ensure patients make follow-up appointments. Additionally, there is an additional risk of being withdrawn from the Standard of Care treatment if they are randomized into the experimental condition. Benefits of this procedure included improved functional internal rotation following surgery and the potential to change clinical practice.

Data analysis

The primary outcome (i.e., functional internal rotation at six months) will be compared between the groups using Mann-Whitney U test. Other range of motion data (i.e., forward elevation and external rotation at the side), pain VAS, ASES, SANE, PROMIS, and VR-12 will be compared using either independent t-test or Mann-Whitney U test depending on the normality of data distribution of each variable. The correlations between functional internal rotation and all other variables will be analyzed using Spearman rank correlation or Pearson correlation.

Patient and public involvement

Patients who undergo RTSA often have limitation of functional shoulder internal rotation following surgery. However, there are no literature that discuss conjoint tendon lengthening as a possible therapeutic intervention. The current research question was developed to address this, and patients were not involved in the design, recruitment, or conduct of this study. The future results of this trial will be available through publication in a peer-reviewed journal, and at meetings if applicable.

ETHICS AND DISSEMINATION

Safety

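### Randomization at enrolment, with nothing withholding the arm from the single unblinded surgeon, lets component choice and subscapularis repair be decided with the arm known

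*Combined protocol and SAP*

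**What the plan says.** **Timing and mechanism of randomization.** Recruitment and consent places randomization at enrolment: "Once a participant agrees to participate, and meets all inclusion criteria, they will be enrolled and randomized into one of two groups". Treatment allocation adds only that "a computer randomization system will be used to allocate patients to receive either of two groups". Neither section says when the result reaches the surgeon.

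**Blinding.** Study design states that "neither surgeons nor participants will be blinded to treatment allocation". The Abstract says that a single surgeon performs all the operations. The Discussion lists the lack of blinding as a limitation and justifies it on the ground that a surgeon cannot be blinded to the technique being used.

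**Order of the operation (Intervention).**
- Components come first: "The sizes and offsets of the components will be chosen based on each" individual's local anatomy, which the sentence says will differ between patients.
- The subscapularis is then repaired "whenever there is a repairable subscapularis tendon". No criterion for repairable is given.
- The arms part only later: "After definitive implantation of the prosthesis is completed, and the subscapularis tendon is reattached, the investigative step will take place".
- Of the steps up to final implant selection, the section says: "Each of these surgical steps will be performed in all patients regardless of whether they are in the control or investigative group".

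**Link to the primary outcome.** The Background lists component features associated with better internal rotation, among them "a decreased glenosphere size". The Safety section records the principal investigator's impression that patients given the lengthening do better, internal rotation in particular.

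**The concern.** One surgeon, who has a recorded expectation about the technique, may know each patient's arm while making two patient-specific judgements that precede the trial intervention. The protocol links at least the first of these, component choice, to the primary outcome.

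If those judgements drift with the arm, in either direction, the difference between groups at six months mixes the effect of lengthening with the effect of the drift. The primary analysis is an unadjusted Mann-Whitney test (Data analysis), so it cannot separate the two. Component sizes, offsets and repair status appear in neither the baseline list nor the outcome list, so the planned data would not show whether the arms were balanced on them.

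**Working it through.** **1. The procedural check.** No figure in the plan decides this point. It rests on setting the sections in order of time.

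| Step | Section | Could the surgeon know the arm? |
|---|---|---|
| Consent, enrolment, randomization | Recruitment and consent; Treatment allocation | Yes, nothing prevents it |
| Choice of component sizes and offsets | Intervention | Yes |
| Subscapularis judged repairable or not | Intervention | Yes |
| Lengthening, or straight to closure | Intervention | Necessarily |

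Only the last row requires knowledge of the arm. The reason given in the Discussion, that technique cannot be hidden from the surgeon, applies to that row alone. The documents do not say that the surgeon is told early; they simply leave it open.

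**2. The plan's own figure.** The sample size section gives 32 per group, 80% power and 5% type 1 error, but no effect size, SD or sidedness, so 32 cannot be reproduced. Solving backwards, two-sided, by the normal approximation:

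d = √(2/32) × (1.960 + 0.842) = 0.25 × 2.802 = 0.70 SD.

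For a Mann-Whitney test on normal data the efficiency is 3/π, so the effective n is 32 × 3/π = 30.6 per group. With the noncentral t distribution (df = 2 × 30.6 − 2 ≈ 59, critical value 2.00), the effect giving 80% power is 0.729 SD.

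**3. Illustration of what a shift would do.** Let b be an assumed arm-related shift in the primary outcome, in SD units. The noncentrality is:
- with no true effect: b × √(30.6/2) = 3.91b;
- with a true effect of 0.729 SD and an opposing shift: 3.91 × (0.729 − b).

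| Assumed shift b | 3.91b | Rejection rate, no true effect | 3.91 × (0.729 − b) | Power, shift opposing a true effect of 0.729 SD |
|---|---|---|---|---|
| 0 | 0 | 5.0% | 2.85 | 80% |
| 0.03 | 0.12 | 5.2% | 2.73 | 77% |
| 0.10 | 0.39 | 6.7% | 2.46 | 68% |
| 0.18 | 0.70 | 10.6% | 2.14 | 56% |

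A shift in the same direction as a true effect would raise the rejection rate and overstate the benefit instead.

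**4. Check on the approximation.** A simulation of 20,000 trials used a normal variable cut into seven levels, with assumed category shares, and a tie-corrected Mann-Whitney test. It gave 4.6% at b = 0, 6.7% at 0.10 and 11.6% at 0.20, where the formula gives 12.0%. The formula is adequate for a seven-level outcome. The shifts of 0.03 and 0.18 were not simulated.

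Every value of b is an assumption. None comes from the documents, and none is a bound.

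**The case against.** The strongest reply is that the operation is already constrained. There is one surgeon and one named implant system, the approach is standard, the steps are common to both arms, and component choice is governed by local anatomy, which has nothing to do with the arm. This is a real partial mitigation: it narrows the room for drift. It does not hide the arm, and it fixes which steps are done rather than the judgement within them.

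Further points on that side:

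- **Subscapularis.** No section says that repair affects internal rotation. That is correct, and no such effect is assumed here. Repair matters as a second judgement that can be made with the arm known; the outcome link that the documents supply is for component features.
- **The authors' own view of the cause.** The Background goes on to say that internal rotation often stays limited despite favourable component features, and that the authors suspect soft tissue. This weakens the expected size of a component effect but does not withdraw the association.
- **Source records.** Operative notes and the scheduled radiographs might allow some of these items to be recovered later. That is fair. The gap is that no collection and no reporting by arm is planned.
- **Disclosure.** Non-blinding is already declared, and unblinded participants and assessors may be the larger problem. Both are true, and delayed release does nothing for either. But the disclosure treats the surgeon's knowledge as unavoidable throughout, when it is unavoidable only at the last step.

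**Conclusion.** The concern holds. Randomization at enrolment, an unblinded single surgeon, patient-specific judgements made before the arms part, and the absence of any provision to withhold the arm are all in the text. It is a risk the design leaves open, not a bias shown to exist.

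Its size and direction cannot be derived from the documents. If the surgeon does not learn the arm early, or if choices do not move with it, nothing changes. The illustrative figures rest on assumed shifts, a two-sided test, full follow-up of 32 per group and an approximately normal underlying outcome. Confidence is high that the safeguard is absent; no confidence attaches to any particular consequence. The change is worth making because the risk is avoidable at little cost and cannot be removed once the operations have been done.

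**What to change.** Consent and enrol as planned, but change when the allocation is released:

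1. In Recruitment and consent and in Treatment allocation, state that the assignment is generated or disclosed in the operating room only after definitive implantation, and after the subscapularis has been repaired or judged not repairable, just before closure.
2. Record component sizes, offsets and subscapularis repair status before release, and report them by arm.
3. Amend the limitation in the Discussion to say that the surgeon is unaware of the arm up to that point and unblinded afterwards.

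If the arm is already withheld in practice, the first change only writes that down.

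**Cost:** wording in three places, one computer log-in or sealed opaque envelope per case, and three recorded items. No patients, visits or procedures are added. The downside is a brief pause before closure, with the lengthening suture on hand for every case. For operations already done, only the recording and reporting by arm can be recovered, as far as source records allow.

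### Five patient-reported scores have no planned preoperative value and no between-group test uses a baseline, which costs precision and description but not validity

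*Combined protocol and SAP*

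**What the plan says.** All places are in the Methods of the combined protocol and SAP.

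- **Baseline measures.** The list is introduced by "The following will be collected from all participants preoperatively". Its seven items are age, sex, range of motion, indication, associated injuries, comorbidities, and residence and ambulatory status. The only one that resembles an outcome is "Preoperative functional (operative) shoulder and contralateral shoulder range of motion if applicable". The movements are not itemised.
- **Outcome measures.** The primary outcome is functional internal rotation at six months on a seven-level scale. The secondary schedule begins with "Six weeks: pain VAS". Three months adds ASES, SANE, forward elevation and external rotation. The later visits are "Six months, one year, and two years: pain VAS, ASES, SANE, PROMIS, VR-12, Forward elevation, external rotation at the side". No preoperative time point appears.
- **Data analysis.** "The primary outcome (i.e., functional internal rotation at six months) will be compared between the groups using Mann-Whitney U test". The other motion measures and the scores "will be compared using either independent t-test or Mann-Whitney U test depending on the normality of data distribution of each variable". No covariate, change score or longitudinal model is named. The planned correlations are not between-group tests.
- **Sample size calculation.** For the primary outcome only, "32 subjects are needed per group with a power set at 80%, and with a Type 1 error probability of 5" per cent.
- **Follow-up.** "All participants will be surveilled per standard of care at our hospital for the targeted patient group". This concerns visits after surgery; it does not say whether the clinic records the scores beforehand.

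**The concern.** The Abstract expects better scores in the lengthening group than in the control group. That is a between-group claim in a trial of 64 patients, sized only for the primary outcome, so the precision of the score comparisons matters. A preoperative value of the same measure is usually the cheapest source of precision. For five scores the plan does not provide for one; for motion it lists one and then leaves it out of every test.

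The two gaps differ in kind. Adjustment for motion, and for the primary outcome, can still be written in before analysis, provided the relevant movements were measured. A preoperative pain or function score cannot be obtained once the patient has been operated on. Without it the report also cannot show whether the groups were alike on these scores before surgery, or how far either group moved.

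**Working it through.** **1. Count of comparisons** (PROMIS and VR-12 as one score each). Six weeks: 1. Three months: 5. Six months, one year and two years: 3 × 7 = 21. Total 1 + 5 + 21 = 27.
- No planned baseline: VAS 5 + ASES 4 + SANE 4 + PROMIS 3 + VR-12 3 = 19.
- Motion listed before surgery but not used in a test: forward elevation 4 + external rotation 4 = 8.

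**2. The plan's own figure.** The 32 per group cannot be reproduced, because no effect size, SD, category distribution or sidedness is given. It can only be solved backwards. Assuming a two-sided 5% test with 80% power:

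d = (1.960 + 0.842) × √(2/32) = 2.802 × 0.25 = 0.70 SD

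The noncentral t distribution with 62 degrees of freedom gives 0.711 SD.

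**3. Effect of baseline adjustment.** With correlation r between the preoperative and follow-up values, ANCOVA multiplies the residual SD by √(1 − r²) and uses one more degree of freedom. The documents give no r, so a range is shown.

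| Analysed per group | Unadjusted | r = 0.2 | r = 0.3 | r = 0.5 | r = 0.6 |
|---|---|---|---|---|---|
| 32 | 0.711 | 0.697 | 0.679 | 0.616 | 0.569 |
| 29 (about 10% missing, assumed) | 0.749 | 0.734 | 0.714 | 0.649 | 0.599 |
| 26 (about 20% missing, assumed) | 0.792 | 0.777 | 0.756 | 0.686 | 0.634 |

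Entries are detectable differences in SD units. At 32 per group the 95% CI half-width is 0.50 SD unadjusted and 0.49, 0.48, 0.43 or 0.40 SD adjusted. Expressed as sample size, an unadjusted test needs 32/(1 − r²) per group to match the adjusted precision: 32/0.96 = 33.3, 32/0.91 = 35.2, 32/0.75 = 42.7 and 32/0.64 = 50.

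**4. Primary outcome.** Simulation with 32 per group, 8,000 trials per cell, and a latent normal baseline and outcome cut into seven equal categories. The shift was set so that the Mann-Whitney test has about 80% power. Analysing ranks with the baseline rank as covariate gave 81.0, 82.4, 87.7 and 91.9% at r = 0.2, 0.3, 0.5 and 0.6. An uneven category split gave 80.2, 82.1, 88.1 and 91.6%. Type I error of the adjusted analysis was 4.6 to 5.4%.

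**5. Does the form of adjustment matter?** Simulated power at 32 per group for a location shift of 0.711 SD, with assumed distributions (6,000 trials per cell; r = 0.3 / r = 0.5). The planned route was modelled as a Shapiro pretest followed by the t-test or Mann-Whitney test.

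| Distribution | Planned route | ANCOVA on means | Rank ANCOVA |
|---|---|---|---|
| Normal | 79 / 79% | 82 / 89% | 80 / 86% |
| Exponential | 95 / 95% | 83 / 87% | 96 / 98% |
| Lognormal | over 99% | 84 / 88% | over 99% |

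With roughly normal scores, ANCOVA on means improves on the planned route. With strongly skewed scores it does worse, while the rank-based version keeps the rank test's power and adds the baseline gain.

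**The case against.** The strongest case on the other side has five parts.

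- **Validity is untouched.** A reader might infer that the comparisons are biased, or that the hypothesis about improved scores cannot be tested, without baseline values. Neither follows. Randomization supports a comparison of postoperative values, the hypothesis is between groups, and the plan promises no change-score or responder analysis. Unadjusted two-sample tests are legitimate, if less efficient. This stands in full.
- **The sample size is the main limit.** A reader might infer that the missing baseline is why only differences near 0.7 SD are detectable. With adjustment, 0.57 to 0.70 SD is still needed. The limit comes from 32 per group; adjustment lowers it by 0.01 to 0.14 SD. This stands too.
- **The gain rests on an assumed correlation.** True. That the scores are missing from the list is certain; how much that matters is not.
- **Preoperative motion is listed.** Also true, so nothing is irrecoverable for the 8 motion comparisons or the primary outcome if those movements are measured. The qualifier about applicability most naturally belongs to the contralateral shoulder. The list still does not name the movements, and no test uses them.
- **The clinic may record the scores anyway.** The Safety section mentions, informally, better pain improvement in earlier patients, but it names no instrument. The documents leave this open. Even if the scores are recorded, the analysis section does not use them.

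**Conclusion.** The point holds as a matter of precision and description, and should be addressed. The five scores are absent from the preoperative list, 19 of 27 secondary comparisons have no planned baseline, and the other 8 and the primary outcome are analysed without one.

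The size depends on a correlation that the documents do not give. At 32 per group the saving in detectable difference is about 0.01 SD at r = 0.2, 0.03 at 0.3, 0.10 at 0.5 and 0.14 at 0.6: negligible at the low end, material from about 0.5. For the primary outcome the corresponding power is about 81 to 92%, against 80%, under an assumed latent normal model. These figures also assume a two-sided test, and the score figures assume that all 32 per group are analysed. Only the loss of preoperative values for the five scores is permanent.

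**What to change.** 1. Add pain VAS, ASES, SANE, PROMIS and VR-12 to the preoperative list, or confirm that they are already recorded and will be used. This is the urgent step, since it cannot be made good after surgery.
2. Confirm that preoperative range of motion covers forward elevation, external rotation at the side, and functional internal rotation on the same seven-level scale as the outcome.
3. Pre-specify for each secondary outcome a baseline-adjusted analysis suited to its expected distribution. Where it is roughly symmetric, use ANCOVA or a longitudinal model, with mean difference and 95% CI. Where skew is expected, use a rank-based analysis with the baseline rank as covariate, because ANCOVA on means can lose power there against the planned route.
4. Keep the Mann-Whitney test for the primary outcome and add a baseline-adjusted rank or ordinal analysis as a supporting analysis.

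**Cost.** One extra questionnaire set per patient before surgery; the documents give no completion time. If the three movements are already measured, their use needs only analysis wording; otherwise they must be added to the preoperative examination. Anyone already operated on will have no baseline score, though a longitudinal model that treats baseline as one of the repeated measures can keep them in. If the correlation is low, the gain in precision is small.

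### The primary Mann-Whitney comparison ignores preoperative rotation: the test is valid, but it gives up power and protection against chance baseline imbalance at almost no saving

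*Combined protocol and SAP*

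**What the plan says.** - **Primary analysis (Data analysis).** "The primary outcome (i.e., functional internal rotation at six months) will be compared between the groups using Mann-Whitney U test". No covariate, stratum or change score is named.
- **Outcome scale (Outcome measures).** "Functional internal rotation will be measured based on the highest anatomical level that the" thumb attains, on seven ordered levels.
- **Baseline data (Baseline measures).** The list includes "Preoperative functional (operative) shoulder and contralateral shoulder range of motion if applicable". It does not name functional internal rotation separately, nor say that it is graded before surgery on the seven outcome levels.
- **Allocation (Treatment allocation).** "a computer randomization system will be used to allocate patients to receive either of two groups". No stratification or minimisation is described.
- **Eligibility.** All primary RTSA is eligible. Revisions are excluded, as is "RTSA for acute proximal humerus fracture or fracture sequela". No figure is given for the spread of preoperative rotation.
- **Other analyses (Data analysis).** The remaining motion measures and the scores "will be compared using either independent t-test or Mann-Whitney U test depending on the normality of data distribution of each variable", again unadjusted. Separately: "The correlations between functional internal rotation and all other variables will be analyzed using Spearman rank correlation or Pearson correlation". Those correlations may include the preoperative value, but they do not adjust the treatment comparison.
- **Sample size.** 32 per group for 80% power at 5% type I error, with no effect size, SD or level distribution.

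**The concern.** A preoperative measurement of the same function is the natural candidate for predicting the outcome, and this trial already plans to record something close to it. If it does predict six-month rotation, leaving it out has two consequences.

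First, variation that baseline could explain stays in the error term, so power is lower than the same 64 patients could give.

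Second, only one randomisation will be carried out. With 32 per arm and no described stratification, the arms may start at different levels of rotation, and an unadjusted comparison carries part of that gap into the estimate. Participants and outcome assessors are unblinded. If a visible gap prompted adjustment afterwards, that would be a choice made with the data in hand, even though the statistician is to be blinded to group. Prespecification removes the choice.

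**Working it through.** **Inputs.** From the documents: 32 per arm, 80% power, 5% type I error, seven ordered levels, Mann-Whitney test. Assumed: two-sided testing (not stated); a baseline-to-six-month correlation ρ from 0 to 0.7; allocation unrelated to baseline; and three level distributions (uniform; low-skewed .15/.25/.22/.16/.11/.07/.04; mid-peaked .05/.12/.22/.25/.20/.11/.05).

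**1. The plan's own figure.** The 32 per group cannot be reproduced because no effect is given. Solved backwards, d = (1.960 + 0.842) × √(2/32) = 2.802 × 0.25 = 0.70 SD (normal approximation). Allowing for the Mann-Whitney efficiency of 3/π gives 0.70/√0.955 = 0.72. On the seven-level scale, a latent shift of 0.74-0.75 SD gives 80% Mann-Whitney power.

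**2. Closed-form gain.** Adjustment multiplies residual variance by (1 − ρ²), so power = Φ(0.700/(0.25 × √(1 − ρ²)) − 1.960).
- ρ = 0.2: Φ(2.859 − 1.960) = 81.6%
- ρ = 0.3: Φ(2.937 − 1.960) = 83.6%
- ρ = 0.5: Φ(3.235 − 1.960) = 89.9%
- ρ = 0.7: Φ(3.923 − 1.960) = 97.5%

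**3. Simulation on the seven-level scale.** A latent bivariate normal is cut to seven levels, with 40,000 replicates per cell. Tie-corrected Mann-Whitney is compared with rank ANCOVA, which regresses the outcome rank on arm and baseline rank (64 − 3 = 61 residual df). The last column is the Mann-Whitney sample size with the same simulated power.

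| Latent ρ | Mann-Whitney power | Rank ANCOVA power | Equivalent n per arm |
|---|---|---|---|
| 0 | 80% | 79.2-79.9% | 32 |
| 0.2 | 80% | 80.5-81.0% | 33 |
| 0.3 | 80% | 82.2-82.6% | 34 |
| 0.5 | 80% | 87.7-88.4% | 40 |
| 0.7 | 80% | 95.7-96.0% | 55 |

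These fall a little below step 2 because cutting to seven levels weakens the correlation. Latent 0.3, 0.5 and 0.7 become observed Spearman values of about 0.27, 0.46 and 0.65. Putting those into the step 2 formula gives 82.9%, 88.4% and 95.8%, close to the simulation.

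**4. Overall validity.** Simulated type I error is 4.8-5.2% for Mann-Whitney and 4.9-5.4% for rank ANCOVA.

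**5. Chance imbalance.** The between-arm baseline difference has SD √(2/32) = 0.25 baseline SDs.
- P(gap > 0.25 SD) = P(|Z| > 1) = 31.7%.
- P(gap > 0.5 SD) = P(|Z| > 2) = 4.6%.
- A gap g shifts the unadjusted latent difference by ρ × g. For g = 0.5 SD this is 0.15, 0.25 and 0.35 SD at ρ = 0.3, 0.5 and 0.7.

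Rejection of a true null, by size of the gap:

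| Latent ρ | Mann-Whitney, gap < 0.25 SD (68% of trials) | Mann-Whitney, gap ≥ 0.5 SD (4.6%) | Rank ANCOVA, gap ≥ 0.5 SD |
|---|---|---|---|
| 0.3 | 4.3-4.5% | 8.2-9.1% | 4.4-5.8% |
| 0.5 | 3.3-3.4% | 16.2-17.1% | 4.4-5.8% |
| 0.7 | 1.8% | 27.9-30.5% | 4.4-5.8% |

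The rank ANCOVA range covers all three correlations together. The large-gap cells rest on about 2,000 replicates each. A repeat run with new code gave 9-11%, 17-19% and 30-31% for Mann-Whitney and 4.3-6.8% for rank ANCOVA, which agrees within simulation error. The columns balance: the unadjusted test rejects too rarely when the arms happen to match and too often when they do not, and averages 5%.

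**The case against.** The planned test contains no error. Mann-Whitney suits a seven-level ordinal outcome, it is prespecified at a named time point, and it holds its size.

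The benefit rests wholly on a correlation that the documents do not give, and their text does not point to a high one. The Background says functional internal rotation "is often unsatisfactorily restored or even lost after RTSA", and attributes the limitation to impingement, component geometry or soft tissue. The Discussion names conjoint-tendon tightness as the apparent main limit on extension and, through it, rotation. At ρ of 0.2 to 0.3 the gain is only 1 to 3 points, or one to two patients per arm. The most striking error rates need both the highest assumed correlation and a gap seen in under 5% of trials, and lower rates in well-balanced trials offset them.

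The covariate may also not exist in usable form, since grading on the outcome scale before surgery is not stated. If preoperative levels cluster at the floor (assumed 60% and 30% in the lowest two levels), power falls to about 86% at ρ = 0.5 and 92-93% at ρ = 0.7.

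All of this stands as a limit on size. None of it removes the point: a floored baseline still leaves most of the gain, and at zero correlation the adjustment costs under 1 point of power. The silence on stratification is only silence; if the randomisation system does balance on preoperative rotation, the imbalance figures shrink and the analysis should reflect that balancing.

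**Conclusion.** The concern holds as a loss of efficiency and of robustness to chance imbalance. The planned analysis is neither invalid nor biased.

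The gain from adjustment runs from nothing at zero correlation, through about 8 points of power (8 more patients per arm in Mann-Whitney terms) at latent 0.5, to about 16 points at 0.7. Adjustment also keeps the error rate near 5% whatever baseline gap occurs. These figures assume two-sided 5% testing, an effect that gives Mann-Whitney 80% power at 32 per arm, the level distributions above, and a preoperative value recorded on the outcome scale. Confidence in the direction is high. Confidence in the size is only moderate, because the documents contain nothing from which to estimate the correlation. The trade favours adjustment: the possible gain is material and the worst-case cost is negligible.

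**What to change.** 1. In Baseline measures, state that functional internal rotation of the operative shoulder is graded before surgery on the same seven levels as the outcome. This must come first, because the grading may not be recoverable once a patient has been operated on.
2. In Data analysis, make the primary test a rank ANCOVA: ranks of the six-month level regressed on arm and on the rank of the preoperative level. Keep the unadjusted Mann-Whitney test as a sensitivity analysis.
3. State how a missing preoperative level is handled, for example by assigning the pooled median rank blind to arm, so that no patient is dropped for a missing covariate.
4. Report a baseline-adjusted proportional-odds ratio with 95% CI as a supporting estimate. Say that it comes from a different model and that the rank ANCOVA p-value decides.
5. Analyse forward elevation and external rotation by ANCOVA on their own preoperative values where recorded. The gain there has not been quantified.

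**Cost:** one data-collection line and revised analysis wording, with no added patients or visits. If preoperative rotation turns out not to predict the outcome, the loss is under 1 point of power.
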